#### **6.5.3.1 Liver Safety Assessment**

The following potentially clinically significant criteria in liver function tests for Alkaline Phosphatase (ALP), Alanine Transaminase (ALT), total bilirubin, Aspartate Transaminase (AST) and their combination are defined. The subject's highest value during the investigational period will be used.

Parameter	Criteria
ALT	> 3xULN >> 5xULN >> 10xULN >> 20xULN
AST	> 3xULN >> 5xULN >> 10xULN >> 20xULN
ALT or AST	> 3xULN >> 5xULN >> 10xULN >> 20xULN
Total Bilirubin	> 2xULN
ALP	> 1.5xULN
ALT and/or AST AND Total Bilirubin (*)	(ALT and/or AST > 3xULN) and (Total bilirubin > 2xULN)
ALT and/or AST AND Total Bilirubin AND ALP (*)	(ALT and/or AST > 3xULN) and Total bilirubin > 2xULN and ALP < 2xULN

(\*) Combination of values measured within same sample; ULN: Upper Limit of Normal

The number and percentage of subjects with potentially clinically significant values in liver enzymes and total bilirubin during the investigational period will be presented overall and by dose level.

#### 6.5.4 Vital Signs

The baseline value is the last available measurement prior to the first dose of IP.

Vital signs (systolic blood pressure [SBP], diastolic blood pressure [DBP], pulse, body temperature and weight) will be summarized using mean, standard deviation, minimum, maximum and median by phase, dose level, and visit. Additionally, a within-subject change will be calculated per visit as the post-baseline measurement minus the baseline measurement and summarized by visit.

Tables for potentially clinically significant vital signs will be generated using baseline value and highest post-baseline value for each subject.

The following criteria are defined as clinically significant for each parameter:

Vital Sign Variable	Criteria
SBP	$\geq 180$ mmHg AND $\geq 20$ mmHg change from baseline
DBP	$\geq 105$ mmHg AND $\geq 15$ mmHg change from baseline
Pulse Rate	$\geq 120$ bpm AND $\geq 15$ bpm change from baseline

Vital signs data will be displayed in listings.

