2.1.2.1.6 Infusion-related Reactions

In nonclinical studies with ASP7517, infusion-related reactions (IRRs)/cytokine-release syndrome (CRS) were not seen. However, there are potential toxicities with intravenous infusion immunotherapy and the exact mechanism causing standard infusion reactions is unclear, but most reactions appear to arise from cytokine release from immune-mediated mechanisms [Lee et al, 2014].

The symptoms and signs associated with a standard infusion reaction include fever, shaking chills, flushing and/or itching, changes in heart rate and blood pressure, shortness of breath or chest discomfort, pain in back or abdomen, nausea, vomiting and/or diarrhea and skin rash.

In addition to the signs and symptoms associated with a standard infusion reaction, CRS may result in neurologic signs and symptoms such as mental status changes, confusion and delirium. Renal and hepatic manifestations may include azotemia, elevated transaminases and hyperbilirubinemia, respectively. Coagulation parameters maybe also be affected and manifested by elevated D-dimer and hypofibrinogenemia, with or without bleeding. In addition, tumor lysis syndrome may also be associated with CRS [Lee et al, 2014]. Patients should be closely monitored for IRRs and CRS and appropriately managed per standard of care.

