2.1.2.1.7 Allergic Reactions and Anaphylaxis

Based on the nonclinical data, no signs or symptoms of allergic reaction or anaphylaxis were seen following ASP7517 administration. The signs and symptoms of anaphylaxis overlap with those of standard infusion reactions. However, certain features are highly suggestive of anaphylaxis, such as urticaria, repetitive cough, wheeze, throat tightness and change in voice, angioedema (usually of face, eyelids or lip), hypotension, loss of consciousness, nausea, vomiting, abdominal cramping and diarrhea. Patients should be monitored closely for any signs or symptoms of allergic reaction or anaphylaxis and managed appropriately per standard of care.

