7.2.3 Vital Signs

Blood pressure, radial pulse rate and body temperature will be measured as specified in the Schedules of Assessments [[Table 1](#) to [Table 2](#)]. Blood pressure should be measured prior to other clinical assessments. Whenever possible, the blood pressure determinations should be undertaken at approximately the same time of day for each study visit.

A calibrated blood pressure measuring device should be used for all blood pressure measurements.

Prior to measuring blood pressure, the study subject should be seated in a quiet room for at least 5 minutes, with his/her back supported and feet comfortably resting on the floor.

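### The SAP's vital-sign significance tables cannot flag hypotension (highest values and high-side limits only) and cannot flag fever (no temperature criterion)

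*SAP*

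**What the plan says.** SAP section 6.5.4 defines the significance tables in one sentence: "Tables for potentially clinically significant vital signs will be generated using baseline value and highest post-baseline value for each subject". The criteria that follow have three rows, and a subject must meet both parts of a row:

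- SBP: at least 180 mmHg, and a change from baseline of at least 20 mmHg.
- DBP: at least 105 mmHg, and a change of at least 15 mmHg.
- Pulse: at least 120 bpm, and a change of at least 15 bpm.

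There is no low limit, no use of a lowest value, and no row for temperature. Temperature is nevertheless collected. Protocol section 7.2.3 states: "Blood pressure, radial pulse rate and body temperature will be measured as specified in the Schedules of Assessments". It also enters the general summary in SAP section 6.5.4, where blood pressure, "pulse, body temperature and weight) will be summarized using mean, standard deviation, minimum, maximum and median by phase, dose level, and visit". Within-subject change is summarised by visit as well, and all vital signs are listed.

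The protocol says which signs to expect. Section 2.1.2.1.6: "The symptoms and signs associated with a standard infusion reaction include fever, shaking chills, flushing and/or itching, changes in heart rate and blood pressure". Section 2.1.2.1.7 includes, among the features that point to anaphylaxis, "angioedema (usually of face, eyelids or lip), hypotension, loss of consciousness".

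**The concern.** Vital signs are part of the primary safety endpoint (protocol Table 7). They are taken hourly for up to 4 hours after dosing, in phase 1 on day 1 of cycles 1 and 2 (protocol Table 1, footnote b) and in phase 2 on day 1 of every cycle (Table 2, footnote b). The protocol warns of infusion reactions and anaphylaxis in the same setting, and any grade 4 hypersensitivity reaction interrupts enrolment and treatment during escalation (section 4.1.4).

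The significance table is the one vital-sign output that applies a fixed numerical rule and counts subjects. As written, it omits one direction and one measurement that the protocol names. At stake is the safety report. A table with no flagged subjects could be taken to mean that no one had a marked vital-sign change, when the rule could not have counted a fall in pressure or a fever.

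**Working it through.** The plan gives no figure to reproduce on this point. The check sets the SAP 6.5.4 criteria against the signs named in the protocol.

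**1. Hypotension.** The SBP row is met only if (highest post-baseline SBP ≥ 180) AND (change ≥ 20). Take assumed values for illustration: baseline 130, lowest post-dose value 70, later highest value 140.
- Value used by the table: 140. First condition: 140 ≥ 180 is false.
- Change on the value used: 140 − 130 = +10. Second condition: 10 ≥ 20 is false.
- Reading "change" as an absolute change to the lowest value does not help: 130 − 70 = 60 meets the second condition, but the first still fails, and a reading of 70 could not meet it either.

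So a fall of 60 mmHg is not flagged. The same logic applies to DBP with 105 in place of 180. If a subject also has a high reading that meets the row, the flag is for the high reading and the fall is still not counted.

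**2. Fever.** The cause is different. Fever is a high value, so taking the highest reading would suit it. It cannot be flagged because the criteria contain no temperature row.

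**3. Count.** Criteria able to detect low pressure: 0 of 3. Criteria using temperature: 0 of 3.

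**4. Data affected.** Assuming one reading at each of hours 1 to 4, a fully treated phase 1 subject has 2 doses × 4 = 8 post-dose readings, and a phase 2 subject up to 6 doses × 4 = 24.

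**5. What the other outputs provide.**
- *By-visit summaries (SAP 6.5.4).* The minimum and maximum can expose an extreme reading, but a group minimum does not say how many subjects were low. Protocol section 9.5.3 plans these summaries by time point and SAP 6.5.5 does so for ECGs, whereas SAP 6.5.4 says only by visit. How the several dosing-day readings enter the summary is left open.
- *Listings.* They show every value and count nothing.
- *Adverse-event tables, including the infusion-reaction and immune-related tables (SAP 6.5.2).* They depend on an event being reported. Under protocol section 12.4.1.1 an abnormal vital sign becomes an adverse event if the investigator judges it clinically significant and not due to the underlying disease. A disease-associated finding need not be reported unless it is worse than expected.

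**6. Contrast within the SAP.** For laboratory parameters graded in both directions, section 6.5.3 tabulates both. No reason is given for a one-sided rule for blood pressure.

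**The case against.** The strongest reply is that detecting these events does not depend on this table. Subjects are observed for at least 4 hours after dosing. Clinically significant abnormal vital signs not due to the disease are reported as adverse events. Infusion reactions and immune-related events have their own overview tables, and related non-hematologic events of grade 3 or higher are DLTs, with listed exceptions. Cohorts are small (3 to 8 subjects per phase 1 dose level, and 12 per disease and dose at stage 1 of phase 2), so listings can be read directly. Protocol section 9.5.3 asks only for descriptive statistics and listings; the significance table is an SAP addition. No stopping rule, dose decision or efficacy estimate uses it.

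Most of this stands, and it limits the point to reporting. A reader might infer that hypotension or fever would go unseen in the trial, or that subjects are less well protected. The documents do not support that. A reader might also infer that the table looks only where the protocol gives no warning. That goes too far as well: section 2.1.2.1.6 mentions changes in heart rate and blood pressure without a direction, so the existing upper limits have a purpose.

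The reply does not remove the gap in counting. None of these routes gives the number of subjects with low pressure or fever by a rule that is independent of attribution, and supplying such counts is what a significance table is for.

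**Conclusion.** The point holds as a limited reporting gap with two separate causes. Hypotension cannot be flagged because the tables use the highest value with upper limits. Fever cannot be flagged because temperature has no criterion. It would be wrong to attribute the fever gap to the highest-value rule.

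The conclusion follows from the wording of SAP 6.5.4 and needs no numerical assumption; the blood pressures in the illustration are assumed. How many subjects would be missed cannot be estimated, because neither document gives event rates. Partial coverage elsewhere keeps this a cheap improvement. It does not threaten the trial's conclusions.

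**What to change.** In SAP section 6.5.4:

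- Add a table using each subject's lowest post-baseline SBP and DBP. State that the hourly post-dose readings are included. Flag a subject when the value is below a low reporting limit AND the decrease from baseline is at least 20 mmHg for SBP or 15 mmHg for DBP, matching the change sizes already in use.
- Add a temperature row based on the highest post-baseline value, with a high reporting limit.
- Keep the existing three rows.

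Neither document states a low-pressure or temperature limit, so the sponsor should write both into the SAP before database lock. They are reporting cut-offs and do not alter any clinical management rule.

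The cost is one or two extra tables from data already collected. The downside is that some flags will be incidental, so the tables should be read alongside the adverse-event listings.

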### 6.5.5 Electrocardiograms (ECGs)

The three values of each ECG parameter within a time point from the central reviewer will be averaged to determine time-specific parameter for a subject, and used in summaries.

ECG variables will be summarized using mean, standard deviation, minimum, maximum and median for each cohort and dose level at each treatment visit and time point, including changes from baseline.

Number and percentage of subjects with normal and abnormal results as assessed by central review for the overall interpretation will be tabulated by cohort and dose level at each treatment visit and time point. A shift analysis table showing shift in overall ECG interpretation from baseline to each time point will be provided. The worst of the three overall ECG interpretations will be used as the time-specific overall ECG interpretation for a subject.

The QT interval corrected for heart rate by Fridericia's formula, QTcF, is defined as:  $QTc (F) = QT/(RR)^{0.33}$ , where RR interval is inversely proportional to heart rate (approximately RR = 60/heart rate).

The QTcF interval will be summarized using frequency tables for each treatment visit and time point for values of clinical importance using the range criteria below.

	QTc Interval Criteria Value (msec)	
	Cumulative Category	Interval Category
Normal	≤ 450	≤ 450
Borderline	> 450	> 450 to ≤ 480
Prolonged	> 480	> 480 to ≤ 500
Clinically significant	> 500	> 500

The QTcF interval will also be summarized by the frequencies of subjects with a change from baseline of clinical importance using the criteria identified below. These summaries will be provided for each treatment visit and time point.

Variable	Change from Baseline	
	Cumulative Category	Interval Category
QTc Interval (msec)	<0	<0
	≥ 0	≥ 0 to ≤ 30
	> 30	> 30 to ≤ 60
	> 60	> 60

Number and percent of subjects with 12 lead ECG abnormalities as well as number and percent of subjects whose 12 lead ECG reading changed from normal at baseline to abnormal will be tabulated by phase and dose level at each treatment visit and time point.

### **6.5.6 Pregnancies**

A detailed listing of all pregnancies will be provided.

### **6.5.7 Eastern Cooperative Oncology Group (ECOG) Performance Status**

Number and percent of subjects for each category of the ECOG performance status at each assessment time will be provided. The change from baseline to EOT score will also be summarized. Negative change scores indicate an improvement. Positive change scores indicate a decline in performance.

ECOG will also be summarized using shift table from baseline to post-baseline score for each dose level by visit.

## **6.6 Analysis of Pharmacokinetics**

Cellular DNA load and kinetic parameters will be summarized by using descriptive statistics including n, mean, standard deviation, minimum, median, maximum, coefficient of variation (CV), geometric mean, and geometric CV. Spaghetti and mean time-course of cellular DNA load will be constructed. Pharmacokinetic data from the China cohort will be analyzed separately.

### **6.6.1 Estimation of Pharmacokinetic Parameters**

Subjects with sufficient cellular DNA samples will have kinetic parameter estimates for ASP7517 including calculation of AUC,  $C_{max}$ , and  $t_{max}$  estimated by the pharmacokineticist using a non-compartmental analysis method in reference to Manual for Non-Compartmental Analysis of Pharmacokinetic Data from Studies using PhoenixTM® WinNonlin® (Certara, Saint Louis, Missouri, US) software version 6.4 or higher.

Exploratory analysis between pharmacokinetic parameters and clinical measures (e.g., efficacy or safety) may be performed.

Kinetic parameters will be plotted against dose to make an assessment of their relationship.

## **6.7 Interim Analysis (and Early Discontinuation of the Clinical Study)**

No interim analysis is planned. Safety, pharmacokinetic and other clinical data will be reviewed on an ongoing basis to determine if the study will proceed on to the next dose level/phase. For phase 2, according to the BOP2 design, the futility analysis for efficacy will be performed at the end of stage 1 and stage 2. Twelve subjects will be enrolled at each dose level for each disease type during stage 1 of BOP2. If the response rate does not meet the optimal stopping boundaries, then stage 2 will open and an additional 20 subjects may be enrolled during this stage. Combining the data from stage 1 and stage 2, stage 3 may be opened for an additional 20 subjects for a total maximum sample size of 52 for each disease type, if the response rate does not meet the optimal stopping boundaries after stage 2.

Optimized Stopping Boundaries for AML	
Number of subjects treated	Stop if number of responses ≤
12	1
32	6

AML: acute myeloid leukemia

Optimized Stopping Boundaries for MDS	
Number of subjects treated	Stop if number of responses ≤
12	0
32	4

MDS: myelodysplastic syndrome

The safety in phase 2 will be monitored using Bayesian logistic model based on all DLT data obtained at the time of the analysis for both escalation and expansion cohorts and drug related TEAEs leading to death. Safety monitoring with these models will start when phase 2 is opened. Enrollment in phase 2 may be held based on the following 2 criteria: 1. If the posterior mean of the DLT rate is higher than 30% as indicated by Bayesian logistic model across disease types at a given dose level, then enrollment will be stopped in phase 2 at that dose level and at higher dose levels for that therapy. 2. Additionally, if the posterior mean of the DLT rate is higher than 30% as indicated by Bayesian logistic model in a specific disease type at a dose level, enrollment of that dose level and any higher dose-level will be stopped for that disease type.

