9.1 Sample Size

Phase 1 (Dose Escalation)

The sample size for the dose escalation phase is not based on a statistical power calculation. The number of subjects enrolled will be dependent on the DLT incidence. The estimated number of subjects, a minimum of 6 evaluable and up to 18, should provide adequate information for the dose escalation and safety objectives of the study.

Phase 2 (Dose Expansion)

The sample size in phase 2 is up to 104 subjects per dose level. Each dose level may enroll up to 52 R/R AML subjects and up to 52 R/R higher risk MDS subjects. The response rate is monitored using the BOP2 design. For AML, with assumption of the efficacious CRc rate is 30% and the inefficacious CRc rate is 15%, the statistical power would be approximately 0.83 while controlling the type I error rate at 0.10. For MDS, with assumption of the efficacious CR + BM CR + PR rate is 25% and the inefficacious CR + BM CR + PR rate is 12%, the statistical power would be approximately 0.83, while controlling the type I error rate at 0.10.

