9.4.1.3 Phase 2 Expansion

The CRc rate for subjects with R/R AML and CR + BM CR + PR rate for R/R higher risk MDS are continuously monitored using the BOP2 design [Zhou et al, 2017]. The number of dose levels investigated during phase 2 will be based upon the data from phase 1. Initially, 12 subjects will be enrolled at each dose level for each disease type during stage 1 of BOP2. If the response rate does not meet the optimal stopping boundaries (see table below), then stage 2 will open and an additional 20 subjects may be enrolled during this stage. Combining the data from stage 1 and stage 2, stage 3 may be opened for an additional 20 subjects for a total maximum sample size of 52 for each disease type, if the response rate does not meet the optimal stopping boundaries (see table below). Otherwise, the enrollment at that dose level will be closed.

When the total number of subjects reaches the maximum sample size of 52, it may be concluded that ASP7517 is efficacious if the number of responses is greater than or equal to 12 and 10 for AML and MDS, respectively. The number of subjects in stage 1, stage 2 and stage 3 may be changed according to the optimized stopping boundaries.

Optimized Stopping Boundaries for AML	
Number of subjects treated	Stop if number of responses ≤
12	1
32	5

AML: acute myeloid leukemia

Optimized Stopping Boundaries for MDS	
Number of subjects treated	Stop if number of responses ≤
12	0
32	4

MDS: myelodysplastic syndrome

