#### Phase 2 (Dose Expansion)

The sample size in phase 2 is up to 104 subjects per dose level. Each dose level may enroll up to 52 R/R AML subjects and up to 52 R/R higher risk MDS subjects. The response rate is monitored using the BOP2 design. For AML, with assumption of the efficacious CRc rate is 30% and the inefficacious CRc rate is 15%, the statistical power would be approximately 0.83 while controlling the type I error rate at 0.10. For MDS, with assumption of the efficacious CR + BM CR + PR rate is 25% and the inefficacious CR + BM CR + PR rate is 12%, the statistical power would be approximately 0.83, while controlling the type I error rate at 0.10.

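### The AML futility boundary at 32 subjects is 5 responses in the protocol and 6 in the SAP, so the documents give opposite decisions at 6 of 32; with the protocol's final rule, the SAP boundary gives power 0.80, not 0.83

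*SAP*

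**What the plan says.** Phase 2 monitors each disease type at each dose level with a BOP2 design in three stages. The protocol sets the sizes in section 9.4.1.3: "Initially, 12 subjects will be enrolled at each dose level for each disease type during stage 1 of BOP2", then "stage 2 will open and an additional 20 subjects may be enrolled during this stage", then 20 more, for a maximum of 52.

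The AML stopping table in protocol 9.4.1.3 reads "Stop if number of responses ≤ 12 1 32 5". That means: close the dose level at 1 or fewer responses in 12, or 5 or fewer in 32. The synopsis and section 4.1.5 carry the same table. The SAP has one AML table, in section 6.7, which reads "Stop if number of responses ≤ 12 1 32 6".

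Only the protocol gives a rule for the end of the trial. At 52 subjects the product may be called "efficacious if the number of responses is greater than or equal to 12 and 10 for AML and MDS, respectively".

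Both documents state the same AML operating characteristics. SAP section 3 says "the efficacious CRc rate is 30% and the inefficacious CRc rate is 15%, the statistical power would be approximately 0.83", with type I error held at 0.10, and protocol section 9.1 gives the same figures.

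**The concern.** One cell differs between the two documents: the AML limit at 32 subjects. The AML limit at 12 and both MDS limits (0 of 12, 4 of 32) agree. That cell is a go/stop rule on the AML primary endpoint. If an AML dose level passes stage 1 and has exactly 6 responses in 32, the protocol allows stage 3 to open and the SAP ends enrolment. Choosing between the two rules once a cohort stands at 6 of 32 would mean choosing with the data in view, which defeats the purpose of fixing the rule in advance.

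The second question is whether the stated power can belong to both boundaries. A stricter futility limit with everything else unchanged must lower power, yet both documents state 0.83.

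**Working it through.** **Inputs.** Null and target CRc rates p0 = 0.15 and p1 = 0.30 (protocol 9.1, SAP section 3). Looks at 12, 32 and 52 subjects (protocol 9.4.1.3). Stage 1 limit b1 = 1 in both documents. Stage 2 limit b2 = 5 (protocol) or 6 (SAP 6.7). Success if total responses are at least r = 12 of 52 (protocol 9.4.1.3).

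**Formulas.** Let X1 ~ Bin(12, p), X2 ~ Bin(20, p) and X3 ~ Bin(20, p), independent.

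- Stop at 12: P(X1 ≤ b1).
- Stop at 32: P(X1 > b1 and X1 + X2 ≤ b2).
- Declare success: P(X1 > b1, X1 + X2 > b2, X1 + X2 + X3 ≥ r). This is the type I error at p0 and the power at p1.

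**Reproducing the stated figure.** With b2 = 5 and r = 12, at p = 0.30:

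- stop at 12: 0.0850
- stop at 32: 0.0284
- reach 52 but miss 12 responses: 0.0581
- success: 1 − 0.0850 − 0.0284 − 0.0581 = 0.8285 (0.8286 unrounded)

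This is the stated 0.83. At p = 0.15 success has probability 0.0667, inside the 0.10 limit. As a check on the method, the MDS design (limits 0 of 12 and 4 of 32, success at 10 or more of 52, rates 12% and 25%) gives power 0.835 and type I error 0.078, which also agrees with the stated 0.83. Ignoring the futility looks, 12 or more of 52 would give AML power 0.895, so the stated 0.83 does include them.

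**Alternatives for AML.**

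| Limit at 32 | Success at 52 | Type I error | Power |
|---|---|---|---|
| 5 (protocol) | ≥ 12 (protocol) | 0.067 | 0.829 |
| 6 (SAP) | ≥ 12 (protocol) | 0.059 | 0.801 |
| 6 (SAP) | ≥ 11 (in neither document) | 0.093 | 0.826 |
| 5 (protocol) | ≥ 11 (in neither document) | 0.112 | 0.861 |

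The last row breaks the 0.10 limit, so the stage 2 limit and the final cut-off have to be set as a pair.

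**Where the power goes.** The two rules differ only on paths that pass stage 1 and stand at exactly 6 of 32. At p = 0.30 that has probability 0.0466. From 6 of 32 a dose needs at least 6 responses in the last 20, and P(Bin(20, 0.30) ≥ 6) = 0.584. The loss is 0.0466 × 0.584 = 0.027, which equals 0.829 − 0.801 after rounding. Stopping at the 32-subject look rises from 0.028 to 0.028 + 0.047 = 0.075.

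**Chance of the disputed result, by true CRc rate.**

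| True rate | P(exactly 6 of 32 after passing stage 1) | P(reaching 12 of 52 from there) |
|---|---|---|
| 15% | 0.113 | 0.067 |
| 20% | 0.132 | 0.196 |
| 25% | 0.094 | 0.383 |
| 30% | 0.047 | 0.584 |

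**The case against.** The contradiction itself is not open to dispute, but several points limit its weight.

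- The power shortfall is conditional. The SAP states no final cut-off, and a limit of 6 with success at 11 or more of 52 would meet both stated figures (0.826 and 0.093). This stands as a condition. However, 12 or more is the only final rule in either document.
- The net effect is small: 2.7 points of power. The rise in stage 2 stopping from 2.8% to 7.5% overstates the harm, because about 42% of doses at 6 of 32 would miss 12 of 52 anyway even at a true rate of 30%. At a true rate of 15%, stopping is the desired result; there the SAP limit lowers type I error (0.067 to 0.059) and expected sample size (28.8 to 26.6). All of this stands.
- The SAP presents itself as an elaboration of the protocol, so staff following the protocol would use 5. That weakens the practical risk without removing it, because SAP 6.7 is where the SAP sets out the futility analysis.
- The SAP (version 3.0, 27 June 2023) is later than the protocol (version 7.5, 19 September 2022), so 6 could be deliberate. Its revision history lists no boundary change, and section 3 keeps the power of the old design. The protocol does let stage sizes change, but that does not cover a different limit at the same 32 subjects.

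**Conclusion.** The concern holds. The protocol, in three places, and the SAP, in its only table, give opposite decisions for an AML dose level with 6 responses in 32. The stated power of 0.83 is that of the protocol's design. The SAP limit gives 0.801 under the protocol's success rule of 12 or more of 52, a loss of 2.7 points, and does not raise type I error.

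The case for correction rests on the contradictory go/stop rule for the primary endpoint, together with the missing success threshold in the SAP, rather than on the size of the power loss. The figures assume independent binomial responses and looks at exactly 12, 32 and 52 subjects. That 5 is the intended value is an inference from the three matching protocol tables and the match to 0.83. The documents do not show whether any AML cohort reached 32 subjects.

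**What to change.** In SAP section 6.7, change the AML limit at 32 subjects from 6 to 5. In the same place, add the protocol's final rules: at least 12 of 52 for AML and at least 10 of 52 for MDS. Also correct the cross-reference in SAP section 2.2, which sends the reader to section 6.8 for a table that stands in 6.7. This costs one number, one sentence and one reference in the SAP, with no extra subjects or data.

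If 6 was intended, the change is larger. Amend the three protocol tables, and then either keep 12 or more of 52 and restate AML power as about 0.80, or adopt 11 or more of 52 in both documents (type I error 0.093, power 0.826). Record the reason in the SAP revision history. Either way, settle it before the responses at the 32-subject look are known, or, if they are already known, state in the clinical study report which rule was applied and when it was chosen.
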